This study will be a randomized controlled trial (RCT) of the SMART Connections, a socio-behavioral intervention using an online social media platform (Facebook) designed to improve retention in HIV care services. Participants will be randomized to the online intervention group or control group (standard of care).

The hypothesis being tested with this study is:

YLHIV who participate in SMART Connections will be more likely to be retained in HIV care at 6-9 months after enrollment than YLHIV in the control group.

Secondarily, we will also test the role of social support as a potential mediator of the intervention effects on retention in care:

Among YLHIV enrolled in ART services, those in the treatment group who are exposed to SMART Connections will have greater social support and, in turn, will be more likely to be retained in HIV care services at 6-9 months compared to those in the control group.

Sample Size and Sampling Design 111.

Sample size

Our primary outcome is retention in HIV care. We will need to recruit 250 experimental participants and 250 control participants to be able to detect a 0.125 difference in the cumulative probability of retention at 12months (0.45 in the control group and 0.575 in the intervention group), corresponding to a hazard ratio of 0.69, with 80% power and 5% significance level for a two-sided comparison using the log-rank test. These calculations also assumed exponential times to event and a 10% loss to follow-up.

Sampling and recruitment procedures

Eligible participants will be sequentially recruited from patients who attend clinic visits at the study facility until the total sample size has been achieved. Potential participants will be assessed for eligibility and written informed consent will be obtained from each participant prior to enrollment in the study.

Randomization procedures

A randomization manager from FHI 360, who is not otherwise involved in the study, will prepare a computerized randomization list using permuted blocks before the start of the study. These envelopes will be given to study staff in charge of the enrollment process. These staff will open the randomization envelopes and inform the participant which group s/he has been assigned to. Participants will be randomized in a 1:1 ratio to proceed with the study procedures. The master randomization list will be maintained at FHI 360 and will not be available to study staff.

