3. Participation data and push messages

Topics: Timing and completeness of scheduled intervention activities, posts and comments related to each session

Timing: Ongoing during intervention

Source: Grytics software linked to Facebook groups

Format: Automatically-collected engagement data

Population: Facilitators and participants in all Facebook intervention support groups

4. In-depth interviews

Topics: Experiences related to intervention implementation, challenges, if any, encountered and suggestions for improving the intervention to achieve greater participation.

Timing: endline

Source: Semi-structured interview

Format: For YLHIV: Up to 45 study participants (minimum 12 moderate/high participation in intervention, 12 low/no participation in intervention, and 12 with poor retention in ART care) at endline.

5. Cost data

Topics: Costs for intervention training, materials, supplies, and implementation; facilitator stipends, SBO supervisors to facilitators, monthly meetings for facilitators; costs of implementing inperson support groups by SIDHAS project **Timing: Post-intervention**

Source: Data extraction from study financial records and from SIDHAS financial records Format: Excel spreadsheet **Population: NA**

6. Documentation of personal messages

Topics: Number and reason for personal messages to group facilitator (i.e. question about side effects, question about appointments, etc.).

Timing: During intervention implementation Source: Communication log Format: Paper form to be filled out by facilitator Population: All intervention facilitators

B. Data Management

Data collected during administration of structured questionnaires and clinical data abstraction will be recorded on tablets using Open Data Kit and will be uploaded to a secure, FHI-hosted server. The primary quantitative analyst will download data from the server and conduct regular checks for completeness and accuracy of collected data.

Missing data

All primary analyses will be conducted using complete case analysis, meaning that we will analyze those observations for which complete data exist for the variables included in each analysis. Missingness (missing or refused) of each variable will be assessed using mdesc in Stata. If variables for a model have 5% or greater missingness, we will conduct multiple imputation. See details following each proposed model in sections VI and VII.

C. Created Variables

Retention at endline

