 - [if yes] How often did this happen? (Rarely [1-2 times], Sometimes [3-10 times], Often [more than 10 times])
- Did you or any household member go a whole day and night without eating anything at all because there was not enough food
 - [if yes] How often did this happen? (Rarely [1-2 times], Sometimes [3-10 times], Often [more than 10 times])

Following scoring guidelines, a new variable will be created for each question with the following response options:

- Indicated that this type of food insecurity did not happen (variable=0)
- "Rarely" or "sometimes" (variable=1)
- "Often" (variable=2)

An aggregate score will be created by summing the three new variables. The aggregate score will have a minimum score of 0 and a maximum score of 6. Results at each time point will be represented as mean aggregate score at each time point. We will also present the proportion of participants in each of the following household hunger categories as per the HHS scoring guide:

- Aggregate score 0-1: Little to no hunger in household
- Aggregate score 2-3: Moderate hunger in household
- Aggregate score 4-6: Severe hunger in household

Adherence

Adherence will be dichotomized at baseline and endline (adh_bl,adh_el) based on self-reporting having missed one more medication dose in the past 3 days (q422).

Code:

gen adh_el=.

⁷ Information on scoring the HHS is available from: https://www.fantaproject.org/sites/default/files/resources/HHS-Indicator-Guide-Aug2011.pdf

replace adh_el=1 if if q420==1 | q420==2 | q420==3 | q421==1 | q421==2 | q421==3 | q422==1 | q422==2 | q422==3 | q422==4 | q422==5; 0 otherwise

replace adh_el=0 if adh_el==. & (q420==4 | q420==5 | q420==6 | q421==0 | q422==0)

VL suppression

A dichotomous variable, vl_sup, will be created for each VL measurement instance to indicate virologic failure following the standard definition of virologic suppression being <1,000 cp/mL. The variable will be missing for any instances where VL measures were not available.

HIV knowledge and treatment literacy

HIV knowledge and treatment literacy will be assessed using a set of fifteen true/false questions [q226 – q240] administered at baseline, midpoint, and endline. For each knowledge question, a new variable will be created to more easily quantify correct responses and will be coded as 1 if a correct response was given, and 0 if an incorrect answer, "don't know" response, or refusal was given. For example:

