For adherence and viral suppression at endline, both of which will be dichotomized, we will conduct chisquare tests. We will also explore associations between treatment exposure and secondary outcomes using multiple linear regression models:

1. Social support

Model:	Multiple Linear Regression
Outcomes:	Change in social support score from baseline to endline (ss_avg_chng, individual sub- scales)
Exposures:	Study group (intervention v. comparison)
Covariates:	Age, sex, education at baseline, depression score at baseline, social isolation score at baseline

2. HIV knowledge/treatment literacy

Multiple Linear Regression Model:

Analysis Plan: Using Social Media to improve ART Retention and Treatment outcomes among youth living with HIV in Nigeria - The Youth SMART study

Outcomes: Change in knowledge score from baseline to endline (know chng)

Study group (intervention v. comparison) Exposures:

Covariates: Age, sex, education at baseline

3. Self-reported adherence

Model:	Multiple Logistic Regression
Outcomes:	Adherence at endline
Exposures:	Study group (intervention v. comparison)
Covariates:	Age, sex, education at baseline, household hunger score at baseline, time on ART at baseline, social support sub-scales, adherence at baseline

4. Viral load

Model:	Multiple Linear Regression
Outcomes:	Viral load at endline
Exposures:	Study group (intervention v. comparison)
Covariates:	Age, sex, education at baseline, household hunger score, adherence, time on ART at baseline, social support sub-scales

We will check that the following assumptions of multiple regression are met:

- Independence of observations (i.e. independence of residuals) ٠
- Linear relationships between dependent variable and each independent variable, and between dependent variable and the independent variables collectively. Method: Scatterplots
- Homoscedasticity variance does not change along line of best fit. Method: Plotting studentized • residuals against unstandardized predicted values
- No multicollinearity. Method: Inspect correlation coefficients and VIF values •
- No significant outliers, highly influential points, etc. Method: Exploratory data analysis
- Normal distribution of residuals. Method: Histogram with normal curve fitted, and normal p-plot of residuals

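### The endline viral suppression test uses only participants with a clinic-recorded viral load, a group selected by retention, and so may be biased against an intervention that improves retention.

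*SAP*

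**What the plan says.** **Source and coding.** SAP section IV.A takes viral load results from the clinics' electronic medical records, and the summary table of measures names the same source. Section IV.C (VL suppression) creates a yes/no variable for each measurement, described as made "to indicate virologic failure following the standard definition of virologic suppression being <1,000 cp/mL", and adds: "The variable will be missing for any instances where VL measures were not available". It gives no window that says which measurement is the endline one.

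**Test.** SAP section VI, Objective 2: "For adherence and viral suppression at endline, both of which will be dichotomized, we will conduct chisquare tests". The tests are two-sided at 0.05.

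**Missing data.** Under section IV.B (Missing data), "we will analyze those observations for which complete data exist for the variables included in each analysis". That rule is worded for primary analyses, but no other rule is given for these chi-square tests. Multiple imputation is a secondary analysis, triggered at 5% missingness. It is tied to the Objective 2 regression models, where viral load is the outcome of a linear regression. Neither the adherence nor the viral load imputation list includes retention or care status, and the text expects very little missing data.

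**Planned retention.** SAP section III: "We will need to recruit 250 experimental participants and 250 control participants", with 12-month retention of "0.45 in the control group and 0.575 in the intervention group".

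**Adherence.** It is self-reported at interview. The protocol's Data collection section places the interview at a clinic appointment, but allows up to three further contacts and then a telephone interview.

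**The concern.** A participant who leaves care generates no new clinic viral load. The end-of-study tracing in the protocol checks for transfer and attendance and does not obtain a viral load. Who enters the suppression test is therefore partly decided by the primary outcome, and the two arms are compared within subgroups formed after randomisation.

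The direction of the bias matters. Suppose the intervention works by keeping marginal patients in care, and these patients are suppressed less often than those who would have stayed anyway. Adding them to the measured group lowers the intervention arm's measured proportion, although more of its randomised participants are suppressed. A positive retention result could then sit beside a suppression result that points the other way.

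**Working it through.** **1. The plan's own figure.** Inputs, all from SAP section III: retention 0.45 and 0.575, two-sided 5%, 80% power, and "These calculations also assumed exponential times to event and a 10% loss to follow-up".

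- HR = ln(0.575)/ln(0.45) = 0.693.
- Events (Schoenfeld) = 4 × (1.960 + 0.842)² / (ln 0.693)², rounded up to 234.
- Average event probability over 12 months, with exponential events and 10% exponential dropout = 0.4655.
- Per arm = 234 / 0.4655 / 2 = 251.4, against 250 stated.

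The figure reproduces, so the retention inputs are used below. The plan gives no sample size, power or assumed rate for suppression.

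**2. How many would have a value.** If viral load existed only for those retained at 12 months, 250 × 0.45 ≈ 113 controls and 250 × 0.575 ≈ 144 intervention participants would be measured. The other 55% and 42.5% would not, which is far from very little missing data.

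**3. Measured-only against all randomised, 12-month retention.** Assumptions, not in the documents:

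- 45% of each arm is retained regardless, and 80% of them are suppressed.
- A further 12.5% of the intervention arm is retained because of the intervention, with a proportion s suppressed.
- Nobody out of care has a value.

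Measured-only, intervention = (0.45 × 0.80 + 0.125 × s) / 0.575; control = 0.80.
All randomised, no value counted as not suppressed: control = 0.45 × 0.80 = 0.360; intervention = 0.360 + 0.125 × s.

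| s | Measured-only, intervention | Difference from 80% | All-randomised difference |
|---|---|---|---|
| 0.50 | 73.5% | -6.5 points | +6.3 points |
| 0.60 | 75.7% | -4.3 | +7.5 (36.0% vs 43.5%) |
| 0.70 | 77.8% | -2.2 | +8.8 |
| 0.80 | 80.0% | 0 | +10.0 |
| 0.85 | 81.1% | +1.1 | +10.6 |

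Break-even is at s = 0.80, where the added group is suppressed as often as the others.

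**4. The same at day 270**, the SAP's time point. Under the exponential assumption, with 9 of 12 months:

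- Control retention = 0.45^0.75 = 54.9%; intervention = 0.575^0.75 = 66.0%; added group = 11.1%.
- With s = 0.60, measured-only = (0.549 × 0.80 + 0.111 × 0.60) / 0.660 = 76.6%, a difference of -3.4 points.
- All randomised: 44.0% vs 50.6%, a difference of +6.7 points.

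The chance that the chi-square is significant against the intervention is about 13% in the 12-month example and about 10% at day 270.

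**5. If some people out of care do have a value.** Let a share f of the non-retained be measured, with a proportion q of them suppressed (80%/60% and 12-month retention as in step 3):

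- Control = (0.36 + 0.55 × f × q) / (0.45 + 0.55 × f)
- Intervention = (0.435 + 0.425 × f × q) / (0.575 + 0.425 × f)

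| f | Difference, q = 0.10 | Difference, q = 0.30 |
|---|---|---|
| 0 | -4.3 points | -4.3 points |
| 0.10 | -1.2 | -2.0 |
| 0.20 | +0.9 | -0.4 |
| 0.30 | +2.5 | +0.8 |

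The sign recovers once roughly 20-30% of those lost have a value.

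**6. Adherence.** The same form applies, with f the share of the non-retained who are interviewed. Assuming 85% adherence in those retained anyway, 60% in the added group and 10% out of care, the difference is -5.4 points at f = 0, -2.1 at 0.10, +0.3 at 0.20 and +4.2 at 0.50. In the other settings tried, the sign changed at f of roughly 0.1 to 0.3.

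**The case against.** Four points on the other side carry weight.

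- **Having a value is not the same as being retained.** The 28-day survival variable in SAP section IV.C counts one gap of more than 28 days as loss, even if the person returns. Records are abstracted through 12 months and the suppression variable is made for every measurement. Some people classed as lost may therefore have a usable viral load, and step 5 shows that this matters. The protocol's questionnaire also asks for the last viral load result, although the tables of measures name the medical record as the source.
- **The size rests on assumed rates.** A reader might infer from the example that the sign reverses whenever retention improves. The documents do not support that: they give no suppression rates, the 50-70% range lies below break-even, and an adverse result would usually not be significant.
- **Adherence differs.** A reader might extend the point to adherence as if only people in care were interviewed. The protocol's repeat contacts and telephone interviews mean that this is not established.
- **Counting no value as not suppressed changes the question.** With values only in those retained, the all-randomised difference is 0.125 × s, largely the retention effect rescaled. It also absorbs any difference in testing between arms of an open-label trial. This is a reason not to make it the sole test.

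Imputation is not a good answer to the concern. It is secondary, assumes data missing at random, is specified for the regression models and not the suppression test, and omits care status. It would tend to carry the measured-only difference forward.

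**Conclusion.** The concern holds for viral suppression. As planned, the test compares subgroups selected after randomisation by something close to, though not identical with, the primary outcome. The bias runs against the intervention if the additional retained patients are suppressed less often than those retained anyway and few people out of care have a viral load.

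Under 80% and 60% suppression, and no values out of care, the measured-only difference is -4.3 points at 12-month retention and -3.4 at day 270, where the all-randomised difference is +7.5 and +6.7. The reversal is a possibility that depends on those assumptions, not a prediction. For adherence, the documents support only a request to show who was interviewed.

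**What to change.** In the SAP:

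1. Define the endline viral load window, for example the last value in days 180-365.
2. Beside the complete-case chi-square, report the proportion of all randomised participants with a recorded viral load below 1,000 cp/mL in that window. Count no value as not suppressed, and state how deaths and transfers are counted; censoring does not carry over to a fixed proportion.
3. Show numbers measured by arm and by endline care status.
4. Add care status to the viral load imputation model. This helps only if some people out of care have values; otherwise add a missing-not-at-random sensitivity analysis.
5. Base the suppression conclusion on both analyses.
6. For adherence, report interview completion by arm and care status, and use missing-as-non-adherent only as a sensitivity analysis.
7. State the coding direction of vl_sup, which is named for suppression but described as marking failure, and of adh_el, where 1 appears to mark a missed dose. The first adh_el line, read literally, gives non-respondents 0, while the next limits 0 to those who answered; reconcile them.

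The cost is SAP wording and an added table, from data already abstracted. The downside is that the all-randomised proportion partly reflects retention and routine testing, so absolute proportions are lower. The complete-case result and the numbers measured make that visible.

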The primary population of interest for this study is YLHIV, ages 15-24 years in Akwa Ibom and Cross River, Nigeria. Eligibility criteria to participate in the study include:

- HIV positive and know their status
- Actively on ART for up to 12 months including newly initiating patients
- Age 15 to 24 years
- Can demonstrate basic literacy necessary to participate in online chats³

Exclusion criteria include:

- Unable to attend the initial intervention group meeting for treatment participants
- Currently enrolled in another research study related to HIV service retention or ART adherence
- Critically or severely ill requiring hospitalization or such that the individual is unable to provide informed consent at the time of study recruitment

Sample Size and Sampling Design

Sample size

Our primary outcome is retention in HIV care. We will need to recruit 250 experimental participants and 250 control participants to be able to detect a 0.125 difference in the cumulative probability of retention at 12-months (0.45 in the control group and 0.575 in the intervention group), corresponding to a hazard ratio of 0.69, with 80% power and 5% significance level for a two-sided comparison using the log-rank test. These calculations also assumed exponential times to event and a 10% loss to follow-up.

Sampling procedure and recruitment: Eligible participants will be sequentially recruited from patients who attend clinic visits at the study facility until the total sample size has been achieved. Patients currently attend ART clinic visits monthly. If recruitment extends beyond 8 weeks, alternately, we will ask the health ART clinic point person to identify potentially eligible patients based on eligibility criteria from their facility records and to contact the person by telephone to tell them about the study and, if interested, to invite them to come to the facility if they may be interested in participating in a research study.

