q226 re=1 if q226=1, q226 re=0 if q226=0 | q226=8 | q226=99

At each timepoint, knowledge will be quantified as follows:

know=sum(q226_re-q240_re)/15*100

Changes in knowledge scores from baseline to endline will be quantified as follows:

```
know_chng=know_el - know_bl
```

Responsiveness to particular questions as well as changes from baseline to midpoint, and midpoint to endline, will also be assessed descriptively.

Time on ART

Time on ART at baseline, art_time_bl, will be created based off of medical record data reporting the date the participant started ART as well as the date the participant conducted their baseline questionnaire.

art time bl =q011(from MRE)-today bl (from BL questionnaire)

V. Analysis of participant characteristics

Data from the baseline questionnaire will be cleaned and analyzed descriptively prior to the second round of data collection. Descriptive statistics including means and frequencies will be generated for all quantitative variables collected at baseline in addition to aggregate scores for multiple items measuring potential outcomes such as ART adherence and self-efficacy, social support, retention in HIV services, HIV-related stigma, depression/anxiety, and substance use. A descriptive summary of participant characteristics will be presented by intervention and control groups at all time points. Participant characteristics will include age, marital/relationship status, education, religious affiliation, employment, and food insecurity/household hunger.

VI. Analysis of Study Objectives

Objective 1.

To test the effect of the intervention on the primary outcome, retention in care, we will report Kaplan-Meier cumulative retention probabilities with 95% confidence intervals and plots by study group. The retention probabilities between the groups will be compared with a logrank test stratified by site with a two-sided alpha = 0.05.

The null hypothesis is:

YLHIV who participate in SMART Connections will have the same likelihood of being retained in HIV care at 270 days as YLHIV in the control group.

The alternative hypothesis is:

YLHIV who participate in SMART Connections will be more likely to be retained in HIV care at 270 days than YLHIV in the control group.

Data will be prepared using the stset command:

```
stset timevar, id(id_str) failure(ltfu_28=1) origin(time -0.01) exit(time
```

270)

Where:

```
timevar - time to failure in days, created variable ret_time_28 defined
above
idvar - participant ID id_str

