failvar - failure variable, created ordinal variable ltfu 28 defined above
```

The origin command includes participants with 0 survival time because these participants had the potential to be retained in care during the study period. The exit command specifies that 270 days is the latest timepoint at which we will assess retention.

Kaplan-Meier cumulative retention probabilities at endline with 95% confidence intervals, by study group:

sts list, by(group_itt) ci

Plots by study group:

sts graph, by(group_itt) ci

Log-rank test for difference in retention between groups , stratified by site:

sts test group, strata(facility) detail

Secondarily, we will also conduct the survival analysis described above using the 90 day cutoff variables (i.e. ltfu_90, ret_time_90).

We will also report on the proportion of participants, by study arm, who are retained at 12 months after enrollment. We will use additional regression models (For example, a multivariate Cox proportional hazards model) to explore factors associated with retention in further detail, such as time on ART at enrollment, age, and sex.

If the variables other than retention included in these models have ≥5% missingness, a multiple imputation model will be run as a secondary analysis. Multiple imputation creates multiple sets of plausible values for missing data that reflect the uncertainty about the missing data. The imputation model will include additional variables that are theoretically related to the variables being imputed (Chantala & Suchindra; Stuart, 2009; White, 2011): Age, sex, date of HIV test, date of ART initiation, depression, and social support. We will impute individual items (for example, individual items missing from the social support measure), rather than generated scores. Although there is some controversy as to whether to round categorical variables after imputation (Allison, 2005), we will round the values in each variable in order to facilitate interpretation of results and given expected very small proportion of missing data.

The multiple imputation procedure involves 3 phases (Rubin, 1996; Yuan, 2000):

- 1. The missing data are filled in m times to generate m complete data sets.
- 2. The m complete data sets are analyzed by using standard procedures.

3. The results from the m complete data sets are combined for inference.

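### The SAP formula for time on ART at baseline subtracts the dates in reverse order, so the covariate carries the wrong sign

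*SAP*

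**What the plan says.** SAP section IV.C introduces the variable in words: "Time on ART at baseline, art_time_bl, will be created based off of medical record data reporting the date the participant started ART", together with the date of the baseline questionnaire. The formula follows: "art time bl =q011(from MRE)-today bl (from BL questionnaire"). Read with that sentence, q011 is the recorded ART start date and today_bl is the baseline interview date.

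The Protocol (Study Population) fixes the possible range through the eligibility criterion "Actively on ART for up to 12 months including newly initiating patients".

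The variable is used in three places in SAP section VI:

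- Objective 1: additional regression models, with a Cox model as the example, will "explore factors associated with retention in further detail, such as time on ART at enrollment, age, and sex".
- Objective 2, model 3 (logistic, self-reported adherence at endline), covariates: "Age, sex, education at baseline, household hunger score at baseline, time on ART at baseline, social support sub-scales, adherence at baseline".
- Objective 2, model 4 (linear, viral load at endline), covariates: "Age, sex, education at baseline, household hunger score, adherence, time on ART at baseline, social support sub-scales".

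**The concern.** A variable called time on ART should increase the longer a participant has been treated. This one decreases. Nothing elsewhere in the SAP takes an absolute value or changes the sign.

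The reversed order does not look like a house convention. In the same section, retention time for a participant who died is the death date minus the baseline date, the completeness flag uses the first visit date minus the baseline date, and the knowledge change is endline minus baseline. Each takes the later quantity first.

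What is at stake is the interpretation of one coefficient. The Protocol's own programme data (Background, Nigeria) show losses concentrated soon after ART initiation: two-thirds of those lost had gone within three months, and losses fell considerably after the first year. A reader would therefore look at the direction of this term. With the formula as written, a model in which longer treatment goes with better retention would print a hazard ratio above 1. The p-value and fit statistics would give no warning, because they are the same either way.

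**Working it through.** The documents give no figure that depends on this variable, so there is no published number to reproduce. The check evaluates the formula and then follows the sign through a model.

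**Inputs**
- Formula as written: q011 - today_bl (SAP IV.C).
- Intended quantity: elapsed time, today_bl - q011 (from the variable's name and the sentence before the formula).
- Eligible range: ART started 0 to about 365 days before baseline (Protocol, Study Population).

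**Step 1: values over the eligible range**

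| ART start relative to baseline | As written (days) | Elapsed time (days) |
|---|---|---|
| same day | 0 | 0 |
| 1 day before | -1 | 1 |
| 30 days before | -30 | 30 |
| 183 days before | -183 | 183 |
| 365 days before | -365 | 365 |

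A start recorded 7 days after baseline, for example through a record discrepancy, gives +7 as written.

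**Step 2: effect on a coefficient**

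Let x be elapsed time and b its true coefficient. The model sees -x. Since b·x = (-b)·(-x), the fitted coefficient is -b and every fitted value is unchanged. In the Cox and logistic models the ratio becomes exp(-b) = 1/exp(b). In the linear viral load model the slope changes sign. With an assumed hazard ratio of 0.90 per month (not a figure from the documents), 1/0.90 = 1.11.

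**Step 3: check in a fitted model**

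A Cox model was fitted to one simulated data set under both definitions. All settings are assumptions: 500 participants in two equal arms; about 20% same-day starters and the rest spread evenly over 1 to 365 days; a baseline hazard of 0.003 per day; log hazard ratios of -0.37 for the intervention arm and -0.002 per day on ART; and follow-up cut at 270 days. Covariates were arm, time on ART in months of 30.44 days, and age.

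| Quantity | As written | Corrected |
|---|---|---|
| Log HR per month on ART | +0.067 | -0.067 |
| HR per month on ART | 1.070 | 0.935 |
| p-value for time on ART | 0.0005 | 0.0005 |
| Arm coefficient | -0.221 | -0.221 |
| Age coefficient | 0.017 | 0.017 |
| Log-likelihood | -1085.35 | -1085.35 |

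Of the 500 values as written, 399 were negative and 101 were zero. Only the sign of the time-on-ART term changes.

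**Step 4: where the variable does not enter**

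The Kaplan-Meier estimates and the facility-stratified log-rank test (SAP VI, Objective 1) use only group, facility, retention time and loss status. The imputation list for the Objective 1 regressions names the date of ART initiation, not this derived variable.

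**The case against.** The strongest reply is that this is a notation slip with little reach. The sentence before the formula states the intended quantity plainly. The line carries bracketed source notes and is not runnable Stata. An analyst who tabulated the variable would see almost every duration negative and correct it. No information is lost, since a change of sign recovers the result exactly. In the adherence and viral load models the exposure of interest is study group, which is not affected. All of this stands, and it is why the point is minor. It does not make the written rule correct: the line is the SAP's only definition of the variable.

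Some stronger readings are tempting, but the documents do not support them:

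- A reader might infer that the variable is negative for every participant. It is not: newly initiating patients are eligible, and a same-day start gives zero.
- A reader might infer that a reported association with retention is reversed. The SAP reports none and commits to none. It offers time on ART as one example factor in exploratory models, and the reversal needs the line to be run literally and the negative values to go unnoticed.
- A reader might infer that groups cut by time on ART, such as more than three months, would be empty. The SAP sets no such cut.

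**Conclusion.** The derivation is wrong as written. It yields the negative of time on ART, with an eligible range of about -365 to 0 days in place of 0 to 365. Used literally, it reverses the sign of one coefficient in the exploratory retention regressions and in two Objective 2 models, and it inverts the corresponding hazard or odds ratio. The primary comparison is unaffected. So are the arm effects, p-values and fit wherever the term enters linearly.

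The conclusion rests on reading q011 as the ART start date. The text implies this, but no codebook entry is given. The 0.90 hazard ratio and the simulation settings are illustrations; the sign reversal does not depend on them. The point is minor.

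**What to change.** In SAP section IV.C, define art_time_bl = today_bl - q011 and state that the unit is days. Add a check that values fall between 0 and about 365, and say how a start date recorded after baseline will be handled, since the corrected formula would make those values negative. If model results are to be presented per month, give the conversion.

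The cost is one edited line and one data check. Design, sample size, data collection and the primary analysis are untouched. If any model has already been run with the variable as written, changing the sign of that coefficient, or taking the reciprocal of its ratio and of its confidence limits (which then swap places), recovers the correct result where the term enters linearly.
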